10.3.2 PDILI laboratory measurements

The number and percentage of participants with elevated liver function tests (the criteria for which are defined in [Table 13-7](#)) will be summarized over all visits.

In addition, the number and percentage of study participants with potential hepatotoxicity with and without symptoms potentially associated with hepatitis or hypersensitivity, and the number and percentage of participants meeting laboratory criteria for PDILI will be summarized over all visits.

Percentages in these summaries will be relative to the number of participants with at least one assessment on or after the first dose of BRV in EP0132.

All scheduled, unscheduled, EDV, DTV and SV assessments occurring on or after the first dose in EP0132 will be included in these summaries. This includes both central and local laboratory measurements. If, however, a central and local laboratory measurement is recorded for a participant on the same calendar day, only the central laboratory measurement will be considered in the summary tables. Percentages will be relative to the number of study participants with at least one assessment on or after the first dose of BRV in EP0132.

Liver function laboratory results for participants with one or more elevated liver function tests will be listed. Criteria for elevated liver function tests can be found in [Section 13.1.5](#). In addition, [Section 13.1.5](#) contains the criteria for PDILI and Hy's Law. The liver function laboratory results listing will include AST, ALT, total bilirubin, and new ratio (nR). The listing will also indicate whether the participant met the criteria for Hy's Law and whether symptoms of hepatitis and hypersensitivity were present. The nR is calculated as the ratio of ALT or AST (whichever is higher) divided by ALP, where ALT, AST, and ALP are expressed as multiples of their upper limits of normal (ULN). Lifestyle for study participants with PDILI will be listed and will include alcohol and illicit drug use within the previous 6 months. Additionally, family medical history will be listed for participants with PDILI. Serum pregnancy tests and urine drug tests will be listed as described in [Section 10.3.1](#). Finally, a listing will be presented including whether the

participant took any potentially hepato-toxic medications that may have contributed to the PDILI event, their most recent study medication administration, single dosage amount, whether the participant discontinued study medication, and the reason for discontinuation of study medication.

In addition, figures including both central and local laboratory measurements, will be provided for the following:

- Shift in liver function tests from N01269 Baseline to maximum value post-first dose in EP0132 (including those at EDV, DTV, SV, and unscheduled visits) for AST, ALT, ALP, and total bilirubin, expressed as multiples of the ULN. The figure will be presented in the form of scatter plots.
- Maximum total bilirubin value versus maximum ALT value (post-first dose in EP0132 and including EDV, DTV, SV, and unscheduled visits), expressed as multiples of the ULN. The figure will be presented in the form of a scatter plot.
- Individual time course plots for participants meeting Hy's Law criteria including ALP, ALT, AST, and total bilirubin. Figures will be presented in the form of line plots with all variables overlaid on the same plot (separate plots for each participant) with values expressed as multiples of the ULN. The N01269 Baseline will be displayed on the plot.

10.4 Vital signs, physical findings, and other observations related to safety

10.4.1 Vital signs

Systolic blood pressure (SBP), diastolic blood pressure (DBP), pulse rate, temperature, and respiratory rate are assessed at MEV, FEV, YEV, EDV, FV, DTV, and SV. Height and body weight are assessed at MEV, FEV, YEV, FV, and EDV.

Observed values and CFB for each measurement will be summarized at each scheduled visit. Body weight and height will additionally be included in the summary.

The definition of PCS is described in [Section 3.4](#). Vital signs and body weight PCS criteria are located in [Section 13.1.3](#). The number and percentage of study participants with PCST values for each vital sign (ie, PCST low value, PCST high value) will be summarized for each variable individually over all visits (including unscheduled visits) and by visit separately. Percentages in the overall summary will be relative to the number of study participants with at least one assessment on or after the first dose of BRV in EP0132. Percentages in the by visit summary will be relative to the number of study participants with a measurement at the visit. The number of occurrences of each unique PCST type will be tabulated within each scheduled visit.

A study participant data listing of all observed vital sign, body weight and height values will be presented. The listing will contain columns indicating which values met the criteria for PCS.

10.4.2 Electrocardiograms

ECGs are performed at YEVs, EDV or FV (as applicable), and SV.

Observed values and CFB for each measurement will be summarized at each scheduled visit.

Summaries of shift from N01269 Baseline to each visit will be provided based on the categories normal, abnormal (not clinically significant) and abnormal (clinically significant). Percentages will be relative to the number of study participants with a measurement at the visit.

The observed values and CFB values for the QTcB parameter will be presented descriptively. The definition of PCS is described in [Section 3.4](#). ECG PCS criteria are located in [Section 13.1.4](#). All QTcB measurements (scheduled and unscheduled) will be assessed to determine if they meet PCS criteria. The number and percentage of study participants that meet the criteria for PCST will be presented for QTcB by visit.

QTcB data and findings will be listed by study participant and visit.

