3.3.7 Mapping of assessments performed at EDV

Efficacy and safety assessments at an EDV will be summarized at the corresponding scheduled visit if the assessment was planned at that visit. An assessment is considered to correspond to a scheduled visit if it falls within the protocol-specified visit window. Assessments performed at an EDV that is not within the protocol-specified visit window of a scheduled visit will not be mapped to a scheduled visit. Re-mapped data will be displayed in the by visit summary tables only if the assessment was planned for that particular visit.

If any particular assessment data are already recorded at the given scheduled visit, data from the EDV visit will not be re-mapped. For example, if an EDV is performed within the same protocol-specified visit window as an existing scheduled MEV/FEV/YEV (eg Month 12) and a participant has a particular assessment (eg neurological examination) present at both Month 12 and EDV, then the neurological examination data from the EDV will not be re-mapped to Month 12.

Data will be re-mapped on a ‘per assessment’ basis where assessments are grouped as follows:

- All assessments from the neurological examination
- All assessments from the psychiatric and mental status assessments
- All vital signs assessments (systolic blood pressure, diastolic blood pressure, respiratory rate, pulse rate and temperature)
- All hematology assessments
- All clinical chemistry assessments
- All endocrinology assessments
- All urinalysis assessments
- All ECG assessments
- All EEG assessments

- Height and body weight
- All C-SSRS assessments
- All EpiTrack Junior assessments
- All PedsQL assessments

The groupings above define the measurements that will be retained together for any re-mapping. If at least one data point from a group of assessments is already available at the respective scheduled visit (eg, systolic blood pressure), the data at the EDV will not be re-mapped.

Handling of EEG assessments occurring at EDVs that are not mapped to scheduled visits is described in [Section 3.13.8](#).

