3.3.9 Mapping of assessments performed at UV

Assessments performed at unscheduled visits will not be remapped to any scheduled visit or EDV or FV, except in the following scenarios:

- Unscheduled assessments performed after the last visit in N01269 and on or before the date of the EV in EP0132 ([Section 3.3.6](#))
- Unscheduled assessments performed for participants that remain in EP0132 study beyond 2 years (Month 24) before they complete or withdraw from the study. These unscheduled assessments will be mapped to scheduled visits using the approach outlined in [Section 3.3.7](#). In the situation where there are two unscheduled visits mapped to the same scheduled visit, the visit nearest to the scheduled day as defined in [Table 3-5](#) will be used. If the two unscheduled visits are the same distance away from the scheduled day, the earliest visit will take priority.
 - If an assessment is missing at the mapped visit, the missing assessment may be obtained from the alternative unscheduled visit, only if the entire group of assessments are missing (Assessments will be grouped as specified in [Section 3.3.7](#)). For example, if only systolic blood pressure is present at the mapped visit, diastolic blood pressure, respiratory rate, pulse rate and temperature will not be obtained from the alternative unscheduled visit.

Handling of unscheduled EEG assessments is described in [Section 3.13.8](#).

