4.1.5 Handling of multiple assessments at a visit

If multiple EEGs, central laboratory assessments, ECGs or vital signs are recorded at the same visit, the first non-missing result (according to time of assessment recorded on the eCRF) will be used in summaries by visit. Assessments of PCS criteria will consider all assessments (scheduled and unscheduled) recorded during the period of interest.

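### The QTcB abnormality table is by visit only, so the number of participants who ever had a PCST QTcB is not reported and some cases found off schedule are not counted

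*SAP*

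**What the plan says.** SAP 10.4.2 sets a wide scope for assessment: "All QTcB measurements (scheduled and unscheduled) will be assessed to determine if they meet PCS criteria". SAP 4.1.5 has the same scope for PCS criteria in general: "Assessments of PCS criteria will consider all assessments (scheduled and unscheduled) recorded during the period of interest". The only QTcB PCST table in 10.4.2 is narrower: "The number and percentage of study participants that meet the criteria for PCST will be presented for QTcB by visit".

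The parallel section on vital signs, 10.4.1, gives two presentations; PCST counts there "will be summarized for each variable individually over all visits (including unscheduled visits) and by visit separately". SAP 10.3.1 does the same for laboratory variables. In both, the overall percentage uses participants with at least one assessment on or after the first BRV dose in EP0132.

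Two mapping rules decide which records reach a visit row. For unscheduled visits, 3.3.9 states: "Assessments performed at unscheduled visits will not be remapped to any scheduled visit or EDV or FV". It makes exceptions for assessments on or before the Entry Visit (EV) and for participants who stay beyond Month 24. For early discontinuation, 3.3.7 states: "Assessments performed at an EDV that is not within the protocol-specified visit window of a scheduled visit will not be mapped to a scheduled visit". Even inside a window, EDV data appear in by-visit tables only if that assessment was planned for that visit. SAP 3.3.8 applies the same approach to the Final Visit (FV).

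Protocol Table 1-2 (footnote o) plans an ECG once a year at the YEV, and at the EDV for those who stop early. Protocol 8.1.6 has abnormal ECGs repeated until they settle.

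**The concern.** The SAP flags all QTcB values but names no table that can hold every flagged one. A safety reader will want to know how many participants had a PCST QTcB at any time after the first dose, and that figure is not planned. It cannot be rebuilt from the visit rows. Adding them counts a participant twice if the criteria are met at two visits, and misses one who met them only at an ECG outside the rows.

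With one routine ECG a year, an off-schedule ECG can be a large part of what is known about a participant's QTcB. What is at stake is a possible undercount in one descriptive safety table. No test or decision rule depends on it.

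**Working it through.** The documents state no figure on this point, so there is nothing to reproduce. The check compares the sections and then counts days.

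**1. The three sections side by side**

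| Data | Assessed against PCS criteria | PCST by visit | PCST over all visits, unscheduled included |
|---|---|---|---|
| Laboratory (10.3.1) | all measurements | yes | yes |
| Vital signs (10.4.1) | all (4.1.5) | yes | yes |
| QTcB (10.4.2) | all | yes | none stated |

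SAP 4.1.5 widens what is assessed but creates no table. No other SAP section supplies an overall QTcB count.

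**2. Which ECGs reach a visit row**

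- ECG at a YEV: yes.
- Unscheduled ECG: generally no (3.3.9). For participants who stay beyond Month 24 it is mapped, but only into a window of a visit where an ECG was planned.
- EDV or FV ECG: mapped only if it falls in a YEV window (3.3.7, 3.3.8). The SAP does not say whether a separate EDV row is shown.
- Repeat ECG at the same visit: by-visit summaries take the first non-missing result, while PCS assessment considers all of them (4.1.5). Such a repeat might be counted.

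**3. Days on which an EDV ECG maps**

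Inputs: YEV targets at Day 365 and Day 731 (SAP Table 3-5); window of ±7 days (Protocol Table 1-1); ECG planned yearly (Protocol Table 1-2, footnote o).

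- Month 12: Days 358 to 372 = 15 days.
- Month 24, up to the target day: Days 724 to 731 = 8 days.
- Share: (15 + 8) / 731 = 23/731 = 3.1%. The other 708 days are 96.9%.

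Variations:
- Stopping the count at Day 730: 22/730 = 3.0%.
- Starting at Day 91: 22/640 = 3.4%.
- Ignoring the planned-at-that-visit condition and using the windows of all eight visits: 7 × 15 + 7 = 112 days, 112/730 = 15.3%.
- Third year, where unscheduled ECGs can map: only the Month 36 window qualifies, 15 of about 365 days = 4.1%.

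These are shares of calendar days. They equal shares of EDVs only if discontinuations are spread evenly, and the documents give no discontinuation timing.

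**4. Three illustrative participants**

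| QTcB meets the criteria at | By-visit rows | Overall row, if added |
|---|---|---|
| an unscheduled ECG at Month 8 only | 0 | 1 |
| Month 12 YEV and its later unscheduled repeat | 1 (Month 12) | 1 |
| Month 12 YEV and Month 24 YEV | 1 and 1 (sum 2) | 1 |

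Only the first is missing from the table. The second is already counted. The third shows why visit rows cannot be added.

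**The case against.** The case against has real weight.

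- **Wording.** A reader might infer that QTcB is tabulated at scheduled visits only. The SAP does not say so. It uses that phrase for a different summary ("Observed values and CFB for each measurement will be summarized at each scheduled visit") and says by visit for PCST. The restriction is inferred from the mapping rules.
- **EDV.** A reader might also infer that most EDV ECGs enter no summary. This is not established. SAP 10.4.2 names EDV and the Safety Visit (SV) among the ECG visits, and 3.3.7 excludes only mapping to a scheduled visit. However, 3.3.7 describes by-visit display of EDV data only through mapping, so the point is open.
- **Repeat ECGs.** It is tempting to say that the loss is concentrated in participants with abnormal ECGs, because protocol 8.1.6 generates repeats. A repeat after a PCST value at a YEV loses nobody, since that participant is already in the YEV row. The exposed case is a QTcB that first meets the criteria off schedule. Table 1-2 marks no ECG at Unscheduled Visits, so such ECGs depend on repeats or the investigator's discretion.
- **Other reporting.** QTcB data are listed by participant and visit, and protocol 8.1.6 has clinically significant abnormalities reported as TEAEs. With about 140 participants, the count could be extracted from the listing. This stands, but a TEAE rests on investigator judgement whereas Table 13-6 sets fixed limits. Unlike the vital-signs listing, the QTcB listing is not said to carry a PCS flag.
- **Origin.** Protocol 9.4.1 plans ECG findings as listings and names no ECG PCST summary, so the SAP already does more than required. But 9.4.1 also plans laboratory and vital-sign PCST summaries by scheduled visit only. The SAP added overall counts there and gives no reason for leaving QTcB out.

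**Conclusion.** The concern holds in a limited form. The QTcB PCST table has no overall count, although the SAP assesses all QTcB values and gives that count for laboratory values and vital signs. A participant whose QTcB first meets the criteria at an unscheduled ECG generally has no row. The same may apply at an out-of-window EDV, depending on whether an EDV row is shown. The number who ever had a PCST QTcB is not reported.

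The number of participants affected cannot be estimated from the documents. The 3.1% describes how little of the calendar is covered by YEV windows. A reader might turn it into a claim that about 97% of EDV ECGs are lost; that would need both evenly spread discontinuations and no EDV row, and the documents support neither. The day count also treats Table 3-5 days, which run from the EV, as study days. The Month 24 exception in 3.3.9 is worded by participant rather than by date, so its reach before Month 24 is not fully clear.

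No primary or secondary endpoint is touched. ECG measures are other endpoints under the primary safety objective, defined per visit. This remains a cheap correction worth making because it can change a reported safety count.

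**What to change.** Add to SAP 10.4.2 the number and percentage of participants with a PCST QTcB over all visits, counting unscheduled visits, EDV, FV and SV. Use as denominator the participants with at least one ECG on or after the first dose of BRV in EP0132, as 10.3.1 and 10.4.1 do for their data. Keep the by-visit table.

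Do not label the row on-treatment. The SV comes two weeks after the last dose, and SAP 3.4 defines PCST as any time after the first dose in EP0132.

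The cost is one extra table row from data already collected and assessed. The reported count may be slightly higher.

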10.4.3 Physical examination

A complete physical examination is performed at FEVs, YEVs, EDV or FV (as applicable), and SVs. A brief physical examination is performed at MEVs and UVs. No summaries or listings of physical examination findings are planned. Clinically relevant findings or worsening of previous findings will be recorded as AEs.

10.4.4 Neurological examination

A complete neurological examination is performed at FEVs, YEVs, EDV or FV (as applicable), and SVs. A brief neurological examination is performed at MEVs and UVs. Each examination will be classified as one of not done, normal, abnormal not clinically significant, or abnormal clinically significant. A summary of shift from Baseline at each FEV, YEV, and FV will be provided. Percentages will be relative to the number of study participants with a measurement at the visit. Additionally, a listing of abnormal neurological examinations will be provided.

10.4.5 Psychiatric and mental status

An evaluation of Psychiatric and Mental Status is performed at each FEV, YEV, EDV or FV (as applicable), and SV. Mental status is reported by recording the presence or absence of psychiatric symptoms, mental impairment, and behavioral problems. These are recorded as not done if the assessment for the parameter was not performed. If symptoms are present, these are recorded as abnormal (yes/no), and clinically significant (yes/no). A summary of shift from Baseline at each FEV, YEV, and FV will be provided. Percentages will be relative to the number of study participants with a measurement at the visit. Additionally, a listing of only abnormal psychiatric and mental status examinations will be provided.

[figure not shown]
10.4.6 Assessment of suicidality

Suicidality will be assessed by trained study personnel using the C-SSRS. This will be completed at MEVs, FEVs, YEVs, EDV or FV (as applicable), UVs, DTV, and SV.

For study participants ≥ 6 years of age at the time of enrollment into EP0132, this scale will be used to assess suicidal ideation and behavior that may occur during the study. All study participants who are ≥ 6 years of age will complete the “Since Last Visit” version at each visit unless the participant turns 6 years of age while enrolled in EP0132. If a study participant becomes 6 years of age during the study, the “Already Enrolled” version of the C-SSRS should be completed at the first visit after the study participant’s 6th birthday. Thereafter, the “Since Last Visit” version of the C-SSRS should be completed at all subsequent visits.

Suicidal ideation is defined as an event in any of the following 5 categories:

Suicidal behavior is defined as an event in any of the following 4 categories:

Suicidal ideation or behavior is defined as an event in any of the above 9 categories. A listing of all C-SSRS responses will be provided for any participant with at least one abnormal result. No summaries of these results are planned.

10.5 Non-absence seizures

Non-absence seizure types are described in [Section 3.13.1.1](#).

10.5.1 Non-absence seizure incidence during the study based on locally read 1-hour EEGs

The incidence of each non-absence seizure type will be summarized over the entire Evaluation Period (including unscheduled visits and visits beyond Month 24) and by visit. Summaries by visit will also include scheduled assessment timepoints beyond Month 24, with scheduled assessment timepoints beyond Month 24 included if at least one participant has an assessment at the timepoint. Study participants who experience more than one non-absence seizure type during a visit (ie, POS and tonic-clonic, POS and other seizure, tonic-clonic and other seizure or all three seizure types) will be counted once for each non-absence seizure type. Percentages for the by visit summary will be relative to the number of participants with a 1-hour EEG at the visit with at least 30 minutes of readable EEG time while awake. Percentages for the Evaluation Period will be relative to the number of participants with at least one (scheduled or unscheduled) 1-hour EEG with at least 30 minutes of readable EEG time while awake occurring on or after the first dose of study treatment in EP0132.

10.5.2 Non-absence seizure incidence during the study based on seizure diary

The incidence of each non-absence seizures type observed from the seizure diary will be summarized over the entire Evaluation Period (including unscheduled visits and visits beyond Month 24) and by 3-month period, as defined in [Table 3-3](#); 3-month periods from and beyond Months 25-27 will be included if at least one participant has started the relevant 3-month period. Study participants who experience more than one non-absence seizure type during a 3-month period (ie, POS and tonic-clonic, POS and other seizure, tonic-clonic and other seizure or all three seizure types) will be counted once for each non-absence seizure type. Percentages for the

each 3-month period will be relative to the number of participants who completed their seizure diary on at least 80% of days within the 3-month period. Percentages for the Evaluation Period will be relative to the number of participants who completed their seizure diary on at least 80% of days over the Evaluation Period.

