To investigate the long-term safety and tolerability of BRV in pediatric study participants with CAE or JAE	
TEAEs requiring a change in BRV doseMaximum intensity TEAE experienced (mild, moderate, and severe)Drug-related serious TEAEsFatal adverse events (AEs)TEAEs by maximum relationship (related and not related to BRV)SAEs by maximum relationship (related and not related to BRV) 
Occurrence of other seizure types, including generalized tonic-clonic seizures (GTCS), based on diary or EEG:
 
Non-absence seizures based on 1-hour EEGNon-absence seizures based on diary 
Estimand: the estimand is defined by the following 4 attributes that will be used to define the treatment effect of interest for the other safety analysis:
 
Population: population as defined in the protocol-specified inclusion/exclusion criteria reflecting the target patient population who receive at least 1 dose BRV during the study.Study participant-level outcome: occurrence of events in the list of endpoints above.Intercurrent event handling: the intercurrent event of concomitant medication use is handled by using a treatment policy strategy in which all AE/TEAE data or seizure data (as applicable) are included, regardless of receipt of any concomitant medication.Population-level summary measure: incidence rates. 
The intercurrent event of treatment discontinuation is handled by using a while-on-treatment strategy where observation ends at 14 days after treatment is stopped.

To investigate the long-term safety and tolerability of BRV in pediatric study participants with CAE or JAE	
CFB to each applicable visit in safety laboratory testsCFB to each applicable visit in electrocardiogram (ECG) parametersECG findings at each applicable visit

Table 2-1: Primary objective

Objectives	Endpoints/estimands
	
Physical and neurological examinations findings at each applicable visitPsychiatric and mental status at each applicable visitCFB to each applicable visit in vital signs (blood pressure, pulse rate, body temperature)CFB to each applicable visit in body weight and height

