2.3.3.2 Daily seizure diaries

Data from daily seizure diaries will be collected during the Evaluation Period (from the EV until the EDV or FV as applicable) and the Down-Titration Period for participants who down-titrate. Study participants will record all types of seizures that occur in their diaries and will complete the diaries after each seizure or at least once a day.

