3.3.2 Study periods

For reporting purposes, the Evaluation Period will last from the date of first dose in EP0132 until the FV inclusive, or from the date of first dose in EP0132 until the EDV inclusive for study participants who prematurely discontinue the study. The Evaluation Period may be truncated at the Month 24 YEV for the reporting of the absence seizure freedom based on seizure data (diary and EEG). It is expected that the first dose in EP0132 will be taken in the evening of the EV. For

participants who complete the study at the FV, the Overall Period will include the Evaluation Period only. Otherwise, for participants who are not required to down-titrate as a dose of 1mg/kg/day (50mg/day for study participants with body weight $>50\text{kg}$) is reached at the FV or EDV, the Overall Period will include the Evaluation Period and Safety Period. Otherwise, the Overall Period will include the Evaluation Period, Down-Titration Period and Safety Period.

For study participants who discontinue BRV treatment following the EDV or FV and a dose of $>1\text{mg/kg/day}$ ($>50\text{mg/day}$ for study participants with body weight $\geq 50\text{kg}$) is reached at the EDV or FV respectively, the BRV dose will be reduced by a maximum of half the dose every week for a maximum of 4 weeks until a dose of 1mg/kg/day (50mg/day for study participants with body weight $>50\text{kg}$) is reached (Down-Titration Period). A DTV will be performed at the end of the Down-Titration Period, and study drug will be discontinued at the DTV. Otherwise, for study participants who will discontinue BRV treatment following the EDV or FV and a dose of 1mg/kg/day (50mg/day for study participants with body weight $>50\text{kg}$) is reached at the EDV or FV respectively, down titration will not be applicable.

After 2 weeks free of study drug (Safety Period), study participants will complete the SV.

The definitions of the Evaluation, Down-Titration, Safety Follow-up, and Overall Periods are provided in [Table 3-2](#). Adverse events are assigned to a study period based on the date of onset. All other measurements are assigned based on the date of assessment.

Table 3-2: Definition of study periods

Period	Definition	Algorithmic rule

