Evaluation Period	From the date of first dose in EP0132 inclusive until: 
• FV inclusive for participants who complete the study, or• EDV inclusive for participants who discontinue the study early	Day of first dose in EP0132 eCRF date inclusive to 
• If the participant completed the study: day of FV eCRF date inclusive;• Else if the participant attended the EDV: day of EDV eCRF date inclusive;• Else if the participant did not attend one of these visits (eg, is lost to follow up): day of last study medication as recorded on the Study Termination eCRF inclusive;• Else if the participant died: the date of death inclusive.
Down-Titration Period	
• From the day after the FV inclusive for study participants who complete the study and	
• If the participant completed the study and subsequently down-titrated: day after the FV eCRF date inclusive;

Table 3-2: Definition of study periods

Period	Definition	Algorithmic rule
	
subsequently discontinue BRV, or
 
From the day after the EDV inclusive for study participants who discontinue the study early and subsequently discontinue BRV 
to
 
the DTV inclusive.
	
If the participant attended the EDV: day after the EDV eCRF date inclusiveIf the participant attended the DTV: day of DTV eCRF date inclusive;Else if the participant did not attend the DTV: day of last study medication as recorded on the Study Termination eCRF inclusive;Else if the participant died: the date of death inclusive.

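### Diary-recorded non-absence seizures during down-titration enter no non-absence seizure table, although both the estimand and the diary cover that period

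*SAP*

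**What the plan says.** **Estimand.** SAP 2.2.1, Table 2-1 lists non-absence seizures by EEG and by diary among the other endpoints of the primary safety objective. For that group, treatment discontinuation is "handled by using a while-on-treatment strategy where observation ends at 14 days after treatment is stopped". Protocol sections 1.1 and 3 carry the same rule for the same endpoints.

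**When treatment stops.** SAP 3.3.2 says of participants who taper: "A DTV will be performed at the end of the Down-Titration Period, and study drug will be discontinued at the DTV". Down-titration lasts at most 4 weeks.

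**Diary.** SAP 2.3.3.2 collects daily diaries in the Evaluation Period "and the Down-Titration Period for participants who down-titrate". Protocol 7.3.2 and footnote c of the protocol's schedule of activities also require this.

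**Summaries.** SAP 10.5.2: "The incidence of each non-absence seizures type observed from the seizure diary will be summarized over the entire Evaluation Period", and also by 3-month period. SAP 10.5.1 uses the same window for EEG, with a breakdown by visit.

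**Where the Evaluation Period ends.** SAP Table 3-2 closes it at the FV for completers and at the "EDV inclusive for participants who discontinue the study early". The Down-Titration Period starts the next day. If neither visit takes place, the Evaluation Period runs to the last study medication.

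**The concern.** The estimand and the table cover different windows. Down-titration is on treatment by the SAP's own definition, so it lies well inside an estimand that continues for 14 days after the last dose. The diary is kept throughout, yet the only planned diary tables close the day before down-titration starts.

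What is at stake is the count of non-absence seizures, including generalized tonic-clonic seizures, while the drug is being reduced. This endpoint belongs to the primary safety objective. A seizure can be written in the diary, confirmed by the investigator and entered in the database, and still be absent from the endpoint's own incidence table.

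The narrowing does not appear to be deliberate. SAP 3.12, which lists changes to protocol-defined analyses, does not mention it. The version history for SAP Amendment 1 explains the removal of the Month 24 cut-off from 10.5.1 by saying that these seizures belong to the primary safety objective and that all of the data should be reported. The FV/EDV cut-off stayed in place.

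**Working it through.** The plan gives no figure to reproduce: the study is descriptive, with no sample size calculation or testing. The check sets the windows side by side in days after FV or EDV.

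1. **Participants who taper.** Down-titration lasts at most 4 weeks: 4 × 7 = 28 days (SAP 3.3.2). The estimand adds 14 days after the last dose: 28 + 14 = 42 days. The Evaluation Period table covers none of these.
2. **How much of that has diary data.** The diary runs to the end of down-titration, so at most 28 of the 42 days (28/42 = 67%) can hold entries. The other 14 days have no diary. The 28 days are a ceiling: at one halving per week, 200 mg/day reaches 50 mg/day after two halvings, so a taper can be shorter.
3. **Participants who stop without tapering.** Under SAP 2.3.1, those already at the end-of-taper dose go straight to the Safety Period. Their gap is 14 days, with no diary, so no recorded diary data are left out.
4. **Participants who continue brivaracetam elsewhere.** They neither taper nor have a Safety Visit, so no recorded diary data are left out.
5. **EEG.** SAP 2.3.3.1 schedules EEGs at the full and yearly evaluation visits and at EDV or FV, and none later. The EEG summary therefore loses essentially nothing.
6. **The 3-month rows.** SAP 10.5.2 takes its periods from Table 3-3, which are plain day ranges from first dose. With an EDV on Day 200, a 28-day taper covers Days 201 to 228, inside the range 181 to 270. Read literally, those days could be admitted. SAP 3.2, 3.13.4, 5.1.1 and 10.2 treat 3-month periods as lying within the Evaluation Period, which would exclude them. The literal reading would also be an unreliable rescue. The 10.5.2 percentages use participants with at least 80% diary completion. If that means 80% of all 90 days, as SAP 3.13.4 applies it to absence seizures for participants who discontinue, 72 days are needed, and this participant has at most 228 − 180 = 48.
7. **Possible size of the undercount (illustration only).** The documents give no rates. Assume that 10% to 50% of 140 participants taper, which is 14 to 70 people. Assume that 2% to 10% of them have a non-absence seizure during the taper and were not already counted for that seizure type. The expected number missed runs from 14 × 0.02 = 0.28 to 70 × 0.10 = 7.0 participants. The chance of missing at least one runs from 1 − 0.98^14 = 0.25 to 1 − 0.90^70 = 0.999.

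**The case against.** **The seizures do not vanish.** A reader might infer that they appear nowhere in the report. The documents do not support that. SAP 8 lists all diary data, and SAP 10.2 summarises TEAEs over the Overall Period, to 14 days after the last dose. Under protocol 7.3.2 the investigator reviews the diary and confirms adverse events from it, and protocol Appendix 3 names convulsions without hospitalization as an example of an important medical event. This stands, and it limits the claim to the non-absence seizure tables. It does not close the gap. The same appendix excludes expected signs of the disease under study unless they are more severe than expected. TEAE tables do not use the three seizure categories of SAP 3.13.1.1, and a listing gives no incidence.

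**42 days would be too large a figure.** Also true: 42 days is the difference between the windows, while recorded data left out amount to at most 28 days, and only for those who taper.

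**The estimand clause may not have been meant for seizures.** Protocol 4.2 ties the while-on-treatment strategy to the TEAE primary endpoint only. Read in context, that sentence separates the two primary endpoints, since the other one carries no such clause. The endpoint tables in both documents attach the 14-day rule to the group containing the seizure endpoints, and the SAP adapted the concomitant-medication wording in that group to mention seizure data. The objection therefore fails, though narrowing the estimand openly would also be a legitimate repair.

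**The Evaluation Period incidence is correct for its label.** True. It is understated only relative to the estimand.

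**Conclusion.** The concern holds for the diary summary. For participants who down-titrate, up to 28 days of required, on-treatment diary data fall inside the Table 2-1 estimand and outside every planned non-absence seizure table. This assumes that the 3-month periods are cut at FV/EDV, as the rest of the SAP implies, and that the FV or EDV was attended.

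The documents do not support three stronger conclusions: that 42 days of recorded data are lost, that the EEG summary is affected in the same way, or that everyone who stops brivaracetam is affected.

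The number of participants involved cannot be derived from the documents; the 0.3 to 7 above rests on assumed rates. Even so, this is a safety endpoint under the primary objective, and the omitted days are those on which the drug is being withdrawn. The correction is cheap and should be made.

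**What to change.** - In SAP 10.5.2, add a Down-Titration Period row and a combined Evaluation plus Down-Titration row. In each, count any participant with a recorded non-absence seizure of each type.
- For the Down-Titration row, use as denominator the participants who entered that period, with diary completion shown alongside. For the combined row, use Safety Set participants with any diary data. A combined row is preferable to an Overall Period row, because the latter includes the Safety Period, where no diary is kept.
- State whether the Table 3-3 periods used in 10.5.2 are cut at FV/EDV.
- In Table 2-1, state that diary observation ends at the DTV for those who taper and at FV or EDV for those who do not. Record this in SAP 3.12, since it departs from the protocol's 14-day wording.
- Separately, reconcile protocol schedule footnote d, under which no diary is dispensed at FV or EDV, with the requirement to keep diaries during down-titration. Otherwise the data for the new rows may not exist.

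The cost is SAP wording and two table rows. Beyond settling the dispensing question, nothing new has to be collected.
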